## Study Protocol

### Objectives

Individuals with cochlear implants struggle to understand speech in the presence of competing sound sources, although there is a wide range of individual variability in speech recognition outcomes across individuals (e.g. Friesen et al. 2001; Stickney et al. 2004). This variability can be attributed to individual differences in the quality of the auditory input that the listener can hear (“bottom-up” factors) and the cognitive abilities of the listener which facilitate the extraction of meaningful information from that input (“top-down” factors).

In quiet conditions, these factors explain much of the individual differences between cochlear implant users. “Bottom up” constraints on auditory resolution, reflected in sensitivity to temporal (Fu 2002; Luo et al. 2008) and spectral (Litvak et al. 2007; Saoji et al. 2009) modulations in acoustic signals, account for about half of the variance in cochlear implant listeners’ speech recognition accuracy in quiet (Won et al. 2011). “Top down” cognitive measures believed to reflect individual differences in attention and fluid intelligence have also been linked to cochlear implant users’ sentence recognition in quiet (e.g. Moberly and Reed 2019).

Interpreting the meaning of correlations between speech recognition and tests of cognitive function is challenging because individual differences in most cognitive tasks have a positive association with one another (Diamond 2013; Miyake and Friedman 2012; Shipstead et al. 2014) and with speech recognition (Dryden et al. 2017). The challenge in interpretation is that previously observed correlations may not arise from a direct relationship between a measured cognitive skill and speech recognition, but rather from an incidental link via some intermediate cognitive skill which is related to both the measured skill and speech recognition. Thus, it is possible that the use of isolated memory tasks (as in previous studies) fails to measure the critical individual differences that govern speech recognition in quiet and in noise. To address this limitation of previous work, this proposal includes a battery of working memory tasks designed to assess individual differences in the ability to store and process information in memory while minimizing confounds that arise from task-specific individual differences.

This proposal focuses on assessing the role of individual differences in working memory in speech recognition in noise. Working memory tasks have been previously shown to predict speech recognition in noise in adults with cochlear implants (Kaandorp et al. 2017; O’Neill, Kreft, and Oxenham 2019), although this relationship has not been consistently observed (Moberly, Houston, et al. 2017). Working memory tasks generally have high reliability (Wilhelm, Hildebrandt, and Oberauer 2013) and avoid issues with interpreting reaction time data (White, Curl, and Sloane 2016; White, Servant, and Logan 2018) and concerns about the validity of underlying constructs (Rey-Mermet, Gade, and Oberauer 2018) that are associated with tasks believed to measure attention.

Working memory is the ability to store and process sequences of information (Akeroyd 2008; Rönnberg et al. 2013). Storage and processing are distinct latent constructs (Unsworth et al. 2009), which are assessed to varying degrees by different memory tasks (Unsworth and Engle 2007). For example, reading span requires switching between processing sentences and recalling unrelated sequences of words or letters (Daneman and Carpenter 1980; Kane et al. 2004), and therefore primarily assesses processing. In contrast, digit span requires maintaining a sequence of numbers in memory and repeating them back in order, which primarily assesses storage. In this proposal we use a battery of quick, reliable working memory tasks that span the range from primarily assessing processing to primarily assessing storage. This will address a gap in current understanding of which elements of working memory facilitate reconstructing degraded speech.

This proposal extends the use of auditory and cognitive predictors to examining individual differences in the ability to track and understand a target speaker in competing noise. In addition to the direct effects of auditory resolution and working memory on recognition of target speech, we propose that auditory resolution and cognitive factors also indirectly affect speech recognition in competing speech by determining the listener’s ability to segregate target speech from competing sound sources. Competing speech can act in two ways: it can overlap with target speech and mask portions of the target which provide speech information (“energetic” masking), and it can intrude on the listener’s processing of the target speech information (“informational” masking) (Kidd et al. 2008; Shinn-Cunningham and Best 2008). Individuals with normal hearing can rely on auditory cues, such as voice pitch, to help separate target and masking speech from one another, but individuals with cochlear implants have difficulty hearing voice pitch differences (Chatterjee and Peng 2008; Deroche et al. 2014) and need large differences between target and masker voices to recognize speech in noise (Meister et al. 2020).

Hypothesis: Stream segregation mediates the relationship between speech recognition in competing speech, auditory resolution and working memory

The premise of this proposal is that individual differences in auditory resolution and cognition affect speech recognition in competing speech directly by affecting recognition of target speech and indirectly by affecting the difficulty of segregating target speech from competing speech. These direct and indirect pathways can be quantified

in a partial mediator model (Baron and Kenny 1986), with stream segregation as the variable that mediates the predictive power of auditory resolution and cognition for speech recognition in competing speech. In this project, we will test whether a partial mediator model describes the relationship between speech recognition in competing speech, stream segregation, and auditory resolution and cognition.

## Design

### Sample Size and Power Analysis

Our preliminary data described below indicate that the measures of auditory resolution and working memory we use will correlate with sentence recognition accuracy with coefficients of at least  $r = 0.5$ . Replicating correlations of this magnitude in the proposed study with  $\alpha = 0.05$  and  $\beta = 0.80$  would require 29 participants. We do not currently have an estimate of the indirect path effect sizes in the mediator model because the stream segregation task we are proposing is novel. For a mediator analysis, the needed sample size to achieve  $\beta = 0.80$  is at least 34 participants if the relationship between auditory resolution, working memory and stream segregation and the relationship between stream segregation and speech recognition in noise have effect sizes of 0.59 (Fritz and MacKinnon 2010). Larger sample sizes would be needed for smaller effect sizes. The limited timeline for this project makes it infeasible to power the study for smaller indirect path sizes (e.g. 71 participants if both effect sizes are 0.39), so the goal of this pilot project will be to provide an estimate of the magnitude of these effect sizes as a basis for determining feasibility of subsequent work. The mediator analysis will still be conducted, but interpretation of non-significant outcomes will be framed within the statistical power of the available sample.

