## Participants

30 participants who lost their hearing and received cochlear implants as adults will participate in this study. We will include unilaterally and bilaterally implanted individuals listening with their everyday hearing configuration. Individuals with residual acoustic hearing better than 60 dBA at any audiometric frequency will be excluded to avoid the confounding the study with the effects of bimodal hearing. Participants with residual hearing in the non-implanted ear will inset an earplug into that ear to further ensure the stimuli are inaudible to that ear. The upper age limit on participants will be 80 years of age, to avoid the rising prevalence of dementia at older ages (Piccirillo et al. 2008) while still including a wide age range. We will attempt to recruit equal numbers of men and women, although we will prioritize including all interested participants over achieving parity. All statistical analyses will be conducted with sex as an additional predictor, although we do not expect sex to affect experimental outcomes.

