#### Predictor 2: Working memory

Preliminary data in young adults with normal hearing (Bosen and Doria, in review) demonstrate a link between a three different memory tasks and recognition of vocoded speech in the presence of a speech masker. These results indicate that the ability of young adults with normal hearing to recognize vocoded speech in speech is sensitive to individual differences in storage and processing. Digit span is also associated with vocoded sentence recognition in quiet in individuals with normal hearing (Bosen and Barry 2020).

In contrast, we did not find a relationship between PRESTO sentence recognition accuracy in quiet and digit span performance in 20 listeners with cochlear implants after controlling for auditory resolution ( $r = 0.25$ ,  $p = 0.28$ ). This finding differs from results in young adults with normal hearing listening to vocoded speech, but additional working memory tasks are needed to determine the reason for this difference. In this study, we will use a battery of quick, reliable memory tasks which assess both storage and processing to determine their relative importance when listening in quiet and in competing speech. These tasks include the three tasks shown to be associated with vocoded speech recognition in competing speech:

*Reading Span* (primarily processing) – Participants alternate between judging if sentences are semantically sensible and storing letters in memory. Between 3 and 7 sentence-letter pairs are presented in each trial, after which participants recall the letters in order. The outcome is the total percentage of letters recalled in the correct position (Conway et al. 2005).

*Serial Digit Span* (primarily storage) – Participants hear a list of between 2 and 9 spoken digits presented with one second between stimulus onsets, then verbally repeat them in order (Bosen and Barry 2020; Bosen and Luckasen 2019). The outcome is the total percentage of digits recalled in the correct position.

*Free Recall* (primarily storage) – Participants read a list of 12 monosyllabic words shown for 750 ms with 250 ms between words, then repeat back words as they remember in any order. The outcome is the average number of words recalled from the list.

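### The planned 30 is below the protocol's own 34 for 0.59 mediation paths, and the 29 rests on an r of at least 0.5 that the pilot data do not print and applies to an unadjusted test

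*Protocol*

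**What the plan says.** The Protocol's Sample Size and Power Analysis section makes two sizing statements.

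- **Correlations.** It says that preliminary data set out later in the document indicate that "the measures of auditory resolution and working memory we use will correlate with sentence recognition accuracy with coefficients of at least" 0.5, and that replicating correlations of this size needs 29 participants.
- **Mediation.** The needed sample "is at least 34 participants if the relationship between auditory resolution, working memory and stream segregation", and the path from segregation to speech in noise, have effect sizes of 0.59. The section then says the timeline makes it "infeasible to power the study for smaller indirect path sizes (e.g. 71 participants if both effect sizes are 0.39". It calls the project a pilot to estimate these effects and promises that "interpretation of non-significant outcomes will be framed within the statistical power of the available sample".

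The Participants section says that "30 participants who lost their hearing and received cochlear implants as adults will participate in this study" and that "All statistical analyses will be conducted with sex as an additional predictor".

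The pilot data on memory are under Predictor 2. In young adults with normal hearing, the data "demonstrate a link between a three different memory tasks and recognition of vocoded speech in the presence of a speech masker"; no coefficient is printed. For implant users the section reports that "we did not find a relationship between PRESTO sentence recognition accuracy in quiet and digit span performance in 20 listeners with cochlear implants". The value printed there is adjusted for the two thresholds: r = 0.25, with p = 0.28.

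SAP Step 2 compares models holding only the two modulation thresholds with models that also hold the memory components kept from Step 1. It states no effect size or power.

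**The concern.** There are three gaps between the sizing text and the rest of the plan.

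1. Only paths smaller than 0.59 are called infeasible, so a reader will take 0.59 as covered. The protocol's figure for 0.59 is 34 and the plan is 30. The two numbers are never compared.
2. The 29 is for a simple correlation, whereas the memory test in SAP Step 2 is adjusted. The same unadjusted r can become a much larger or a much smaller partial r, so the 29 does not tell the reader what Step 2 can detect.
3. A reader who follows the pointer to the pilot data finds no coefficient of 0.5 for memory, and no unadjusted coefficient for either threshold.

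At stake is how null results are read. The protocol promises to frame non-significant mediation results by the available power but gives no power at 30. A null memory result in Step 2 could be set against an r of 0.5 whose task and population are not given, and against a sample size for a different test.

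**Working it through.** **Inputs.** Protocol, Sample Size: r = 0.5, alpha 0.05, 0.80 (labelled beta, read as power), 29; 34 at paths of 0.59; 71 at 0.39. Participants: n = 30, sex in every analysis. Predictor 1: R² = 0.64, betas -0.76 (spectral) and -0.47 (temporal), 20 implant users. Predictor 2: adjusted r = 0.25, n = 20. SAP Step 2: digit span correlates -0.36 and -0.15 with the spectral and temporal thresholds; thresholds are expected to explain about half the variance and to be uncorrelated with memory.

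**1. Reproducing the 29.** Fisher z, two-sided: N = ((1.960 + 0.842)/atanh(0.5))² + 3 = (2.802/0.5493)² + 3 = 29.01. The figure reproduces (power 0.7998 at 29, 81% at 30). There is no arithmetic error.

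**2. Mediation at 30.** Simulated single-mediator model with equal paths, no direct effect and other predictors uncorrelated; both paths must reach p < 0.05 (joint significance). The documents do not say how the 0.59 is scaled, so two scalings are shown: unit residual variances / standardised paths.

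| n, paths | no other predictors | 3 others | 4 others |
|---|---|---|---|
| 34, 0.59 | 77.6% / 84.9% | – | – |
| 30, 0.59 | 69.5% / 77.9% | 61.9% / 71.5% | 59.1% / 69.6% |
| 30, 0.39 | 25.4% / 29.3% | 20.0% / 23.8% | 19.0% / 21.9% |

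At n = 71 with 0.39 paths the result is 78.0% / 81.9%. The protocol's 34 and 71 are therefore consistent with the simulation and are not disputed. With unit residuals, a bias-corrected bootstrap gives about 78% at 30 and 83% at 34.

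**3. Step 2 at 30.** Three covariates (two thresholds and sex), one memory component: power = Φ(atanh(r)·√(30 - 3 - 3) - 1.960), where √24 = 4.899. At partial r = 0.50: 0.5493 × 4.899 - 1.960 = 0.731, giving 76.8%.

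| partial r | 0.25 | 0.30 | 0.40 | 0.50 | 0.71 |
|---|---|---|---|---|---|
| power | 24% | 33% | 55% | 77% | 99% |

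These are normal-theory approximations. For partial r from 0.25 to 0.50, simulated F tests give 24.5%, 34.1%, 56.1% and 78.2% with one component, and 17.8%, 25.4%, 44.2% and 67.7% with two. A quasi-binomial model on 152 keywords (residual SD 0.4-0.9 on the logit scale, an assumption) gives 22-23%, 28-32%, 49-54% and 71-75%. A fixed-predictor noncentral F is more favourable: about 27% at 0.25 and 86% at 0.50.

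**4. What an unadjusted 0.5 becomes after adjustment** (sex taken as unrelated).

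- On Step 2's own expectation: 0.5/√(1 - 0.5) = 0.707, power 99%.
- On the pilot correlations, with the Predictor 1 betas assumed standardised, a linear model and the same 20 people throughout:
  - Correlation between thresholds: (0.64 - 0.76² - 0.47²)/(2 × 0.76 × 0.47) = -0.1585/0.7144 = -0.22.
  - Digit-span variance explained by the thresholds: (0.36² + 0.15² + 2 × 0.36 × 0.15 × 0.222)/(1 - 0.222²) = 0.185.
  - Part of the digit-span correlation carried by the thresholds: 0.76 × 0.36 + 0.47 × 0.15 = 0.344.
  - Scale factor: √(0.36 × 0.815) = 0.542.
  - Partial r: (0.5 - 0.344)/0.542 = 0.29, power 31%.

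**5. What the printed figures imply unadjusted** (same assumptions).

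- Digit span: 0.344 + 0.25 × 0.542 = 0.48.
- Spectral: -0.76 + 0.47 × 0.222 = -0.66.
- Temporal: -0.47 + 0.76 × 0.222 = -0.30.

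**6. Uncertainty of the adjusted 0.25 at n = 20.** The 95% interval is tanh(0.2554 ± 1.96/√17) = -0.22 to 0.62, or -0.25 to 0.64 if two covariates are counted (√15).

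**The case against.** The protocol is candid. It says that no estimate of the indirect paths exists, calls the project a pilot, and commits to reading null mediation results in light of power. No sentence claims that 0.59 paths are powered, and the shortfall is four participants. The 29 is offered for replicating correlations, not for Step 2, which concerns speech in quiet and prepares for the mediation analysis. All of this stands, and it keeps the point small. It does not close the gap: the protocol's framing commitment needs a power figure at 30, and none is given.

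Two stronger readings are tempting and are not supported.

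- A reader might infer that the pilot contradicts r = 0.5 for memory. It does not. The 0.25 is a partial correlation with a wide interval, and on the stated assumptions it corresponds to an unadjusted value of about 0.48. On the same route, the measure clearly short of 0.5 is the temporal threshold.
- A reader might infer that Step 2 has only about 24% power. That follows only if the partial r really is 0.25. On the SAP's own expectation, an unadjusted 0.5 gives 99%.

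**Conclusion.** The point holds as a minor correction to the sizing text.

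- **Firmest part:** 30 is below the protocol's own 34, so by its own figure 0.59 paths do not reach 80% power. The loss is modest with one predictor and larger once the other predictors enter. Its size depends on path scaling, the test used and uncorrelated predictors, none of which the documents fix.
- **Also firm:** the 29 is correct but covers an unadjusted correlation only, and no power is stated for the adjusted memory test.
- **Conditional part:** the claim of at least 0.5 is not shown for memory and looks doubtful for the temporal threshold. The implied unadjusted values depend on standardised betas, a linear model and one common pilot sample.

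Nothing here shows that the sample size is wrong for a declared pilot.

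**What to change.** Revise the wording of the Sample Size and Power Analysis section; n stays 30.

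1. State that 30 is below the quoted 34. Give approximate mediation power at 30 for 0.59 paths: about 70-78% with one predictor by joint significance, depending on path scaling, and about 59-72% with three or four other predictors. Use these figures when framing non-significant mediation results.
2. State that 29 applies to an unadjusted correlation. Give Step 2 power at 30 over the whole range of partial r in the Step 2 table above, labelled as a normal-theory approximation with three covariates and one component, and lower if two components are kept. Say that an unadjusted 0.5 becomes about 0.71 under Step 2's expectation and about 0.29 (31% power) under the pilot correlations.
3. For each measure said to reach 0.5, give the unadjusted pilot coefficient, task and population, and limit the claim to measures that reach it. Report the adjusted 0.25 alongside, labelled as a partial correlation and not as a replacement for the unadjusted value.

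The cost is a few sentences. Enrolment and analyses do not change; the stated support becomes less favourable or less certain in places.

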## Participants

30 participants who lost their hearing and received cochlear implants as adults will participate in this study. We will include unilaterally and bilaterally implanted individuals listening with their everyday hearing configuration. Individuals with residual acoustic hearing better than 60 dBA at any audiometric frequency will be excluded to avoid the confounding the study with the effects of bimodal hearing. Participants with residual hearing in the non-implanted ear will inset an earplug into that ear to further ensure the stimuli are inaudible to that ear. The upper age limit on participants will be 80 years of age, to avoid the rising prevalence of dementia at older ages (Piccirillo et al. 2008) while still including a wide age range. We will attempt to recruit equal numbers of men and women, although we will prioritize including all interested participants over achieving parity. All statistical analyses will be conducted with sex as an additional predictor, although we do not expect sex to affect experimental outcomes.

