### Step 1: Determine the covariance structure of the memory battery

Performance across memory tasks should have a correlation of  $r \approx 0.3$  (Engle et al. 1999; Shipstead et al. 2014), which reflects their common reliance on storage and processing constructs in memory. We will use principal components analysis to examine the loading of task outcomes onto common dimensions. It is possible they will all load onto a single working memory factor (similar to Rönnberg et al. 2016), or they could load onto two orthogonal factors that represent storage and processing (Unsworth and Engle 2007). Principal components with an eigenvalue greater than one will be included in subsequent steps and the remaining components will be discarded as measurement noise.

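### The planned 30 participants are fewer than the 34 the protocol cites for mediator paths of 0.59, and the text does not say so

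*Protocol*

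**What the plan says.** The protocol's Sample Size and Power Analysis section gives three sample sizes.

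- For correlations of r = 0.5, at alpha 0.05 and a target of 0.80 (written as beta, but it can only mean power), the study "would require 29 participants".
- For the mediator analysis at the same target, the number needed "is at least 34 participants if the relationship between auditory resolution, working memory and stream segregation" and the path from stream segregation to speech recognition in noise both have effect sizes of 0.59.
- For both paths at 0.39, the number is 71.

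On feasibility it says: "The limited timeline for this project makes it infeasible to power the study for smaller indirect path sizes". It states that no estimate of the indirect paths exists yet, that the pilot is meant to estimate them, that the mediator analysis will be run anyway, and that "interpretation of non-significant outcomes will be framed within the statistical power of the available sample".

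The next section, Participants, fixes enrolment: "30 participants who lost their hearing and received cochlear implants as adults will participate in this study". The SAP gives no sample size or power. Neither document compares 30 with 34 or gives mediator power at 30.

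**The concern.** The sample-size section names a number for paths of 0.59 and then limits its admission of low power to paths smaller than that. The natural inference is that the 0.59 case is covered. With 30 participants it is not, by the protocol's own figure.

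This concerns the study's stated hypothesis, since the Objectives section says "we will test whether a partial mediator model describes the relationship between speech recognition in competing speech, stream segregation" and the auditory and cognitive predictors. If the mediator result is not significant, a reader who relies on the text could take it as evidence against paths as large as 0.59, believing the study had 80% power to detect them. The promise to interpret such results within the available power gives no number, and it follows a sentence that places the shortfall only at smaller paths.

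**Working it through.** **Inputs.** From Sample Size and Power Analysis: r = 0.5, alpha 0.05, power 0.80, N = 29; paths 0.59 with N = 34; paths 0.39 with N = 71. From Participants: N = 30. Assumed, because the documents do not state them: a two-sided test at 0.05 for the mediator analysis, and the scale of the path effect sizes.

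**Step 1: the 29.** By Fisher's z, n = ((1.960 + 0.842) / atanh(0.5))² + 3 = (2.802 / 0.5493)² + 3 = 29.01. This reproduces 29. At N = 30, power is Φ(√27 × 0.5493 − 1.960) = Φ(0.894) = 0.81. Enrolment of 30 therefore fits the correlation sizing.

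**Step 2: the comparison.** 30 ≥ 29, but 30 < 34. The shortfall is 34 − 30 = 4, and 4/34 = 12%. This step needs no assumption.

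**Step 3: a model close to 34 and 71.** Take one predictor X, a mediator M = aX + e₁ and an outcome Y = bM + e₂, with unit residual variances and a = b. Mediation is declared when a is significant in M on X and b is significant in Y on M and X. This matches the separate path tests in SAP Step 3. Simulated power (100,000 replicates):

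| N | both paths | t critical values | normal critical values |
|---|---|---|---|
| 34 | 0.59 | 0.77 | 0.80 |
| 71 | 0.39 | 0.78 | 0.79 |
| 30 | 0.59 | 0.69 | 0.73 |
| 30 | 0.39 | 0.25 | 0.29 |

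The first two rows come close to the protocol's 80%. With t critical values, 80% at 0.59 is reached at about N = 36, so the match is approximate.

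**Step 4: hand check.** On this scale a path of 0.59 is a correlation of 0.59/√(1 + 0.59²) = 0.508, with atanh(0.508) = 0.560. At N = 30 the first path has power Φ(√27 × 0.560 − 1.96) = 0.83. The second, with X partialled out, has Φ(√26 × 0.560 − 1.96) = 0.81. The product is about 0.68. At N = 34 the same sum gives 0.88 × 0.87 ≈ 0.76. Both are close to the t column.

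**Step 5: why this is not the power of the planned analysis.** The planned model has two modulation thresholds, at least one memory component ("Principal components with an eigenvalue greater than one will be included in subsequent steps") and sex ("All statistical analyses will be conducted with sex as an additional predictor"). At N = 30 and paths of 0.59, changing one set of assumptions at a time (t / normal critical values where two figures are shown):

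- four extra predictors with no explanatory value, independent of the tested predictor: 0.59 / 0.64;
- the same four, each correlated 0.3 with the tested predictor: 0.49 / 0.54;
- three independent extras explaining 50% of the residual outcome variance and 30% of the mediator residual: 0.81 / 0.83;
- one predictor, unit residual variances, other tests: 0.56 (Sobel), 0.68 (percentile bootstrap), 0.76 (bias-corrected bootstrap);
- one predictor, 0.59 read as fully standardised, no direct effect: 0.78 / 0.81;
- the same with a direct effect of 0.3: about 0.91 / 0.93.

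The standardised reading without a direct effect gives 0.85 / 0.87 at N = 34, so under this test it does not reproduce 34. These are examples and do not bound the power. The generalized linear models of SAP Step 2 were not simulated.

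**The case against.** The strongest reply is that nothing here contradicts anything. The 34 is conditional on an effect size that the protocol says it cannot estimate. It is never adopted as a target, and 80% mediator power is never claimed. The sizing that the preliminary data support is 29, and 30 meets it. The study is called a pilot whose aim is to estimate the paths, and non-significant mediator results already carry a caveat about power. The 30 and the 34 stand in adjacent sections, so any reader can compare them.

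Most of this stands. It makes the point a missing disclosure and keeps it minor. It does not remove the implication. By saying that only smaller paths cannot be powered, the text places 0.59 on the powered side, and the caveat gives no figure to correct that.

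Two stronger readings are tempting, and the documents support neither.

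- A reader might infer that the protocol breaks a sample-size commitment and must enrol 34. No such commitment is made.
- A reader might infer that mediator power is known to be about 70%, or lies in some definite range below 80%. The documents give neither the effect-size scale nor the mediation test. They also leave open how far the other predictors correlate with the tested one. SAP Step 2 reports earlier correlations of −0.36 and −0.15 between the thresholds and digit span, not significant, and the plan expects none. Reasonable choices put power at 30 on either side of 80%.

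**Conclusion.** The point holds as a minor gap in the text. Planned enrolment is 4 below the number the protocol cites for paths of 0.59, and the wording suggests that this case is covered. That comparison rests on printed figures alone and is certain. The figures 29, 34 and 71 are not in dispute.

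The size of the power loss is much less certain. The values of 0.69 to 0.73 at paths of 0.59, and 0.25 to 0.29 at 0.39, hold for one predictor, unit residual variances, a joint-significance test and two-sided 0.05. They illustrate the gap on a model close to the protocol's own numbers and are not an estimate for the planned analysis. The pilot aim and the existing caveat limit the harm to how a non-significant mediator result would be read.

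**What to change.** In Sample Size and Power Analysis, add a statement that the planned 30 participants cover the 29 needed for correlations of 0.5 but are fewer than the 34 cited for mediator paths of 0.59, so 80% mediator power is not claimed at 0.59 or below.

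Optionally, add one figure labelled as an illustration: about 0.69 (t) to 0.73 (normal critical values) at N = 30 for paths of 0.59, and about 0.25 to 0.29 for 0.39, with the assumptions of the one-predictor test stated. If it is added, say that power for the planned model depends on the effect-size scale, the test, and the correlation and explanatory value of the other predictors, and could be well below or above 80%. No range should be printed as if it bounded the planned model.

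This changes text only; enrolment and analysis stay as planned. The cost is that the implied mediator power looks slightly less favourable. In return, the caveat on non-significant results has a reference point fixed before the data are seen.
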